9.7 Reporting urgent safety measures

Not applicable

10 STATISTICS AND DATA ANALYSIS

10.1 Sample size calculation

This is a feasibility study and therefore recruitment target is not based on a sample size calculation, rather it is based on practical constraints and the length of the study.

10.2 Planned recruitment rate

We aim to recruit around 50 participants over a period of 6-8 months.

10.3 Statistical analysis plan

A statistical analysis plan will be finalised prior to data lock.

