2 RATIONALE

Recently, technological developments in wireless 'wearable' devices have enabled real-world, real-time measurement of physiological functioning. Remote measurement of respiratory, cardiovascular, and motor function has the potential to detect opioid overdose automatically and reliably (Goldfine, 2020). However, currently available wearable devices have no ability to detect respiratory depression and have limited utility for use as regulated medical devices. Existing chest-worn vital sign sensors are not practical or economically viable for individual use in the community. In addition, little research into the efficacy of remote overdose detection has been conducted. A chest sensor that reliably detects the overdose breathing signature could alert the emergency services and save lives, when fully developed and used in the community. Qualitative study results indicate that this technology would be positively accepted by people who use drugs (PWUD) (Tas, 2023).

The PneumoWave DC Mobile chest biosensor is a small cylindrical device (40mm diameter 14mm height) that sticks onto the chest using a small plastic patch (an ECG sticker) and measures chest motion. PneumoWave are developing an Alert algorithm (that will be incorporated in the DC Mobile system) that will detect reduced chest movement linked to Substance Induced Respiratory Depression (SIRD). To gather device utility and wearability feedback, and refine the Alert analysis algorithm a study is required on patients at high risk of SIRD to capture chest motion during times when possible consumption events might be occurring, where absence or presence of overdose can be externally verified.

Over a six to eight month period, we aim to capture approximately 50 participants known to use opiate drugs, including opioid injection, wearing the device for multiple nights in supported accommodation centres in the UK. Participants will consent to wear the chest-worn device during their residence at the supported accommodation. Chest motion data will be collected on the device securely and pseudo-anonymously (i.e. study ID will be used; no personally identifiable information will be stored alongside chest motion data) and streamed to a secure cloud.

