4 STUDY DESIGN

This is an observational study. It will not incorporate any randomisation or intervention. Participants' health care and the management of any potential SIRD event will not be altered by the procedures of the protocol.

People who use drugs often live in supported accommodation, either for short periods or over a period of years. Many may continue to use drugs while on these premises. To stay at these premises people must be registered as a resident. Short term residents must register before they take up accommodation. Potential participants will be opportunistically recruited by staff working in these premises who are trained to fully explain the study and take informed consent. Drug use is discussed with residents for their own safety. Accommodation staff engage regularly with this population and will be able to identify those who may be eligible. This lowers the risk of them approaching people who do not use drugs and potentially causing unintentional offence or stereotyping. Some supported accommodations will provide injecting equipment on request. This would identify a potentially eligible participant. Consented participants will be recorded on an enrolment log at each participating site. The enrolment log is for administration purposes only and will only be available to site personnel.

The study will utilise the PneumoWave DC Mobile biosensor and data collection platform which includes a wearable biosensor that attaches to the press-stud on a supplied and approved ECG electrode. The biosensor can be placed in a number of locations on the chest and diaphragm area, and automatically connects to a Data Hub via Bluetooth (Fig. 1). The position of the biosensor should be changed weekly. In this study the Hub will be a mobile computing platform (Application running on a tablet). The tablet will be held in a secure location, remaining in range of connection for the PneumoWave DC Mobile biosensor. The tablet has no functionality beyond running the monitoring app. Participants will be informed of this and the tablet's location in their residence. Please see further details in the Study Assessments section (section 7.4).

Figure 1:

Participants receive the device to wear and a tablet with the DC Mobile app downloaded to record data while they are in their accommodation. The wearable device battery will be changed 1-2 times per week.

Long term residents: monitored for 4 weeks or longer up to 8 months

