8 STUDY DEVICE AND SOFTWARE

8.1 Name and description of investigational medicinal product(s)

The PneumoWave DC Mobile device comprises:

Hardware:

- Small, discreet, chest-worn Bluetooth biosensor (40mm diameter x 14 mm thick) mounting on an adhesive patch (single, off-the-shelf ECG electrode)

Software:

- Participant/Administrator mobile device app including user interface, storing and transmitting biosensor data
- Researcher dashboard to review anonymous historic biosensor data
- Backend cloud data management infrastructure for data storage.

Outwith of PneumoWave DC Mobile, proprietary Alert algorithms for retrospectively analysing data for signs of SIRD.

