10.3.2 Primary outcome analysis

- Biosensor data analysed to determine whether or not an alarm would have been raised (and possibly the timing of the alarm)
- Staff measured outcomes reviewed to categorise whether there was cause for concern about the participant
- Above measures compared to determine either True Positive / False Positive / True Negative / True Positive events
- Sensitivity and Specificity are calculated for the complete data set (ideally with error bars calculated by an appropriate statistical method)

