11.2 Data handling and record keeping

The data management system will be an Excel spreadsheet. Password protected and stored on the University of Dundee server. No personal data will be held on the spreadsheet. This will be a pseudonymised data set, linked back to participants by unique study identifier and the enrolment log held at site. Data will be entered by a TCTU trial coordinator, transcribed from the CRFs, AIR tools and drug diaries collected from the participating sites. Data analysis will be carried out by King's College London (KCL). KCL will receive the entered pCRF data as a pseudonymised excel spreadsheet. Shared via encrypted email.

Interview and focus groups will be digitally recorded. All audio transfers will be conducted via audio recorder to a University (UoD or KCL) secured laptop. The interviews/focus group recordings will then be sent to KCL, who will complete a data sharing agreement with UoD. KCL will remove the audio file and related transcripts from their server within 30 days post transcription. Transcription will be completed by a research fellow at KCL. The transcriber will generate an anonymised transcript of the interview/ focus group recordings. Please note is not possible to safeguard against respondents compromising their anonymity or that of others during an interview/focus group, thus the need to anonymise during transcribing. No identifiable data such as interviewee names or interview locations and times will be attached to the audio file, i.e. all audio files will be labelled with an identifier number (which is only known and can only be linked to potentially identifiable information by the delegated researcher). These participant details including the identification number will be stored in a password protected digital file in University of Dundee/KCL, and only the delegated researcher will have access to this file. Participants will be assigned a unique study ID in order to protect their identity. The interview data will not be explicitly linked to specific clinical data for any participants.

Interview/focus group recordings will be deleted once the transcriptions have been received.

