13.7 Data protection and patient confidentiality

The CI and trial staff will comply with the requirements of the General Data Protection Regulation (EU) 2016/679 (GDPR) and the UK Data Protection Act 2018 or any subsequent amendment or replacement thereof with regard to the collection, storage, processing and disclosure of personal data and will uphold the principles of GDPR in Article 5.

While there is no NHS involvement in the study, the CI and trial staff will adhere to the NHS Scotland Code of Practice on Protecting Participant Confidentiality or local equivalent.

All trial records and data will be managed in a manner designed to maintain participant confidentiality. All records, electronic or paper, will be kept in a secure storage area with access limited to appropriate trial staff only. Computers used to collate data will have limited access measures via usernames and passwords. Age and gender will be the only personal identifiable details held on the Excel data management system.

Personal data or data concerning health will not be released without the existence of a legal basis for processing under Articles 6 and 9 of GDPR, such as official authority 6(1)e or substantial public interest 9(2)g. The CI and trial staff will not disclose or use for any purpose other than performance of the trial, any data, record, or other unpublished, confidential information disclosed to those individuals for the purpose of the trial. Prior written agreement from the Sponsor will be required for the disclosure of any said confidential information to other parties.

Access to collated participant data will be restricted to the CI and appropriate delegated trial staff. PneumoWave will not have access to personal identifiable details.

Published results will not contain any personal data that could allow identification of individual participants.

13.8 Financial and other competing interests for the chief investigator, PIs at each site and committee members for the overall trial management

Not applicable.

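### Section 10.3 asks for the SAP only before data lock, so the rules behind sensitivity and specificity may be settled after sensor output has been compared with staff records

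*Protocol*

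**What the plan says.** **Timing.** Protocol section 10.3 sets one deadline: "A statistical analysis plan will be finalised prior to data lock". It does not tie the SAP to first data access, to the first run of the Alert algorithm, or to the first comparison of the two data sources.

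**Primary analysis.** Section 10.3.2 decides from the sensor data whether an alarm would have been raised ("and possibly the timing of the alarm"). It categorises staff-measured outcomes by whether there was cause for concern, compares the two, and reports sensitivity and specificity.

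**Reconciliation.** Section 10.4 has sensor data reconciled with staff- and participant-reported data. Whatever does not reconcile is excluded.

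**Design and access.** Section 4 says of the study: "It will not incorporate any randomisation or intervention". No blinding is described anywhere. Chest-motion data are "streamed to a secure cloud" (section 2), and section 8.1 lists a "Researcher dashboard to review anonymous historic biosensor data". On paper records, section 11.2 says: "Data will be entered by a TCTU trial coordinator, transcribed from the CRFs, AIR tools and drug diaries collected from the participating sites". Section 13.7 says: "Access to collated participant data will be restricted to the CI and appropriate delegated trial staff". That limits access by role, not by time.

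**Purpose.** Section 2 says the data will serve both to test and to develop further the respiratory signatures, and that the Alert algorithm is to be refined with the help of this study.

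**The concern.** A deadline of data lock protects an analysis when something, usually blinding, hides the result until lock. Nothing described here does that. One group is observed, the sensor record and the staff record can both exist before lock, and section 10.4 calls for them to be brought together. Reconciliation is a cleaning step that would ordinarily come before lock. An SAP signed the day before lock, after that step, would comply fully with section 10.3.

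Four rules determine the two-by-two table: which unit is classified, how close in time an alarm must be to an event, which staff observations count as cause for concern, and which records are dropped as unreconciled. The algorithm version also matters, because the algorithm is still under development. If any of these is chosen once its effect on the table is known, sensitivity or specificity can rise with no change in the device, and a confidence interval computed afterwards does not reflect the choice. Sensitivity and specificity are the planned primary analysis and would be the main evidence on how well the algorithm detects overdose.

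**Working it through.** **1. No figure to reproduce.** The protocol states no expected number of events, target sensitivity, alpha or power. Section 10.1 says that recruitment (about 50 participants) is not based on a calculation. The finding rests on the text; the arithmetic below is only illustrative.

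**2. The text, step by step.**
- Latest permitted time for the SAP: any time up to lock (10.3).
- Step that compares the sources: reconciliation and exclusion (10.4), with no condition that the SAP be signed first.
- Barrier between the two: none described. Access is limited by role (13.7), and no masking of those who categorise staff outcomes is stated (10.3.2).
- Reason to run the algorithm early: the same data are for development as well as testing (2).

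So the order 'compare, then settle the rules' is permitted. It is not stated as the plan.

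**3. Generic effect of choosing among rules.** All inputs are assumed: each of k rules has true sensitivity 0.70 on the same n events, and the rules' scores are correlated through a Gaussian latent variable with correlation ρ. For event i and rule j, detection occurs if √ρ·c_i + √(1−ρ)·e_ij < z(0.70), with c and e independent standard normal. The reported value is the largest of the k observed sensitivities, averaged over 20,000 replicates. Each cell gives the means for ρ = 0.9 / 0.8 / 0.5.

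| Events n | k = 2 | k = 4 | k = 8 |
|---|---|---|---|
| 5 | 0.75 / 0.76 / 0.79 | 0.79 / 0.81 / 0.86 | 0.82 / 0.85 / 0.91 |
| 10 | 0.74 / 0.75 / 0.77 | 0.77 / 0.79 / 0.82 | 0.80 / 0.82 / 0.86 |
| 20 | 0.73 / 0.74 / 0.75 | 0.75 / 0.77 / 0.79 | 0.77 / 0.79 / 0.82 |
| 40 | 0.72 / 0.73 / 0.73 | 0.74 / 0.75 / 0.76 | 0.75 / 0.77 / 0.78 |

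With one pre-set rule (k = 1) the mean is 0.70 throughout. The bias therefore runs from 0.72 − 0.70 = 2 points (2 rules, 40 events, ρ = 0.9) to 0.91 − 0.70 = 21 points (8 rules, 5 events, ρ = 0.5).

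**4. Effect of the exclusion rule alone.** Assume 10 events, 6 detected and 4 missed. Sensitivity = TP/(TP + FN), with Clopper-Pearson 95% limits:
- no missed event excluded as unreconciled: 6/10 = 0.60 (0.26 to 0.88)
- 2 of the 4 excluded: 6/8 = 0.75 (0.35 to 0.97)
- all 4 excluded: 6/6 = 1.00 (0.54 to 1.00)

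This applies only if a disagreement between sensor and staff record can count as a failure to reconcile. Section 10.4 does not say whether it can.

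**The case against.** **Access is not the same as sight of the result.** A reader might infer that both sources are open to the team throughout and that someone can watch sensitivity change with each rule. The protocol does not say so. Section 11.2 names who transcribes the paper records but not when. Section 13.7 restricts collated data to certain roles. The dashboard in section 8.1 is for recordings, and the same section places the Alert algorithms outside the DC Mobile system, for retrospective use. Section 3.1 evaluates the primary outcome at end of study. The effect of a rule becomes visible only if the algorithm is run, linked to staff records and scored before the SAP is final. This stands in full: the protocol neither plans that nor prevents it.

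**Missing definitions belong in the SAP.** The match window, the concern categories and the unit may properly be defined there, and the SAP is not at hand. It may also have been signed well before lock. This stands too. The lack of detail in section 10.3.2 is not the point; the stated deadline is.

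**The simulation does not model the real choices.** It treats the rules as interchangeable scorings of the same events. In practice the concern threshold and the unit change the denominator, a wider match window contains a narrower one, and someone weighing specificity would not simply take the highest sensitivity. This is correct, so the table shows a generic effect and does not estimate bias in this study.

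**It is a feasibility study.** There is no hypothesis test or target, and development on these data is openly intended. So type I error is not at issue. But section 10.3.2 still reports sensitivity and specificity as the primary analysis, and a reader will take them as performance estimates unless development and testing are kept apart.

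**Conclusion.** The point holds in limited form. Section 10.3 lets the SAP be finalised as late as data lock, no blinding or time-based access limit is described, and section 10.4 calls for a reconciliation of the two sources that need not wait for the SAP. The protocol therefore permits the rules behind the primary accuracy estimates to be settled after the comparison they govern. It does not show that this will happen.

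The consequence is possible optimism in sensitivity and specificity. Its size cannot be estimated from the document. The 2 to 21 points for sensitivity rest on assumed values for true sensitivity, number of events, number of rules and correlation, and on always picking the highest sensitivity; weaker selection gives less. Because the remedy costs little and protects the primary estimate, the change should be made.

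**What to change.** Replace the sentence in section 10.3 with wording to this effect:

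- The SAP is signed before any biosensor output is matched or reconciled with any staff or participant record.
- It fixes the classified unit, the alarm match window, the cause-for-concern categories, the reconciliation and exclusion rule of section 10.4, and the algorithm version used for the primary estimate.
- Any later change of rule is labelled post hoc, and any later tuning of the algorithm is labelled development. Either is shown beside the pre-set result.

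Add to section 10.4 that reconciliation starts only after SAP sign-off.

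Cost: a few sentences in the protocol, earlier SAP writing, and less freedom to adapt definitions to what the data look like. Sample size, study procedures and participant care do not change, and algorithm development on these data remains possible under its own label.

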10.3.2 Primary outcome analysis

- Biosensor data analysed to determine whether or not an alarm would have been raised (and possibly the timing of the alarm)
- Staff measured outcomes reviewed to categorise whether there was cause for concern about the participant
- Above measures compared to determine either True Positive / False Positive / True Negative / True Positive events
- Sensitivity and Specificity are calculated for the complete data set (ideally with error bars calculated by an appropriate statistical method)

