3 OBJECTIVES AND OUTCOME MEASURES/ENDPOINTS

To establish that the DC Mobile can be used in a supported accommodation environment to record and retrospectively detect changes in chest movement consistent with respiratory patterns of an accidental drug overdose.

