3.1 Table of endpoints/outcomes

Objectives	Outcome Measures	Timepoint(s) of evaluation of this outcome measure (if applicable)
Primary Objective To capture chest motion data using the PneumoWave DC Mobile system	Evidence reduced chest movement using PW DC Mobile system.	End of study
Secondary Objectives Usability and functionality of the DC Mobile biosensor	Participant reported satisfaction survey, feasibility questionnaire, semi-structured interviews, focus group	Day 0 to end of study
Secondary Objectives Potential SIRD events linked to participant drug use behaviour or existing respiratory condition. Substance use and staff-measured outcomes (including overdose) by attendees of supported accommodation	AIR tool questionnaire, drug use diary, CRF	Day 0 to end of study

[figure not shown]

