Supported accommodation staff will check in weekly with participants to ensure the device is being worn, is working and the associated tablet is also present and in a working condition. Participants will receive £25 per week if these conditions are met (further detailed in Payment section). This will encourage participants to look after the device and tablet as only a limited number of each will be available at each site. Site staff will check in on participants overnight to check the device is being

worn and the app is running and note any potential drug use. Participants will be asked to wear the device for 4 weeks initially, with an option to extend the period, if agreed. This continues until the participant declines to be part of the study any longer or the study end point is reached, whichever is first.

Short term residents: monitored overnight

Participants will receive the biosensor and tablet to use overnight and return in the morning. They will receive £5 for returning both the biosensor and device in the morning. Up to a maximum of £25. If they remain a resident, they will recollect the biosensor and tablet for all nights that they are resident. This continues until the participant declines to be part of the study any longer or the study end point is reached, whichever is first. Site staff will be trained to ask for ongoing consent if there are three or more nights where the participant has not been resident at the supported accommodation, following initial informed consent. Site staff will check in on participants to check the device is being worn and the app is running and note any potential drug use.

Applicable to all residents/participants:

It is not expected that participants will always be at a participating site. When leaving the site, the biosensor should be left behind along with the tablet. The biosensor can continue to collect chest movement data while out of range of the tablet for 10-12 hours, once back in range, data will automatically be sent to the tablet. A light on the biosensor will flash red for the duration of time it is out of range.

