7.4 Study assessments

Participants will answer questions to determine their demographics such as age, BMI and gender at birth. If required, participant will be weighed and measured to calculate their BMI. Participants will be asked if they have any existing respiratory medical conditions. After wearing the biosensor, participants will complete a short satisfaction survey on their experience of PneumoWave DC. Participants should complete this at least once. Participants who stay at the site for a longer period may complete more than one to show fluctuating levels of acceptance. Participants will be asked to complete a drug use diary and an AIR tool to describe their drug use. Drug use and care is discussed with participants so these can be completed in the presence of and with support of, site staff.

During welfare checks, site staff will record any evidence of drug use in the pCRF. If a participant requires intervention due to a potential overdose event, site staff will record this in the pCRF, along with the level of intervention required, if the participant is unresponsive. Where possible the biosensor will be left on the participant during the intervention, and removed once the participant has sufficiently recovered or prior to leaving the facility (i.e. transfer to a medical facility).

A subsection of participants will be asked to partake in semi-structured interviews, lasting no longer than 60 minutes, to describe their experience wearing the device.

A further subsection of participants, including those who may have had an interview, will be asked to take part in focus groups to discuss the PneumoWave DC Mobile and the prototype for the Alert system and the perceived benefits or downsides it may have.

Staff from across all participating supported accommodation will be invited to take part in a semi-structured interview and/or a focus group to discuss their views on, perceived benefits of or barrier to use of the biosensor and DC Mobile system.

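### Staff-recorded potential overdoses with no usable sensor recording appear to fall out of the primary sensitivity, so it describes the algorithm given a recording and cannot show whether the system records overdoses

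*Protocol*

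**What the plan says.** The overall aim in Protocol section 3 has two parts, recording and detection: the system "can be used in a supported accommodation environment to record and retrospectively detect changes in chest movement" of the kind seen in an accidental overdose. The primary objective in the section 3.1 table is "To capture chest motion data using the PneumoWave DC Mobile system".

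The primary analysis in section 10.3.2 has two inputs. The index result comes from the sensor: "Biosensor data analysed to determine whether or not an alarm would have been raised". The reference comes from staff: "Staff measured outcomes reviewed to categorise whether there was cause for concern about the participant". The two are compared to give "True Positive / False Positive / True Negative / True Positive events", and sensitivity and specificity are then calculated on a complete data set that is not further defined. Section 10.4 says that sensor data are reconciled with staff and participant reports, and that what does not reconcile is excluded.

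Staff records do not depend on the sensor. Under section 7.4, "If a participant requires intervention due to a potential overdose event, site staff will record this in the pCRF". Section 4 has staff check that the device is worn and the app is running, and provides for one or two battery changes a week. Section 8.4 assesses compliance from data downloaded from returned devices.

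**The concern.** A potential overdose that staff write down while the sensor has no usable trace has a reference result but no index result. The table has no place for it, and the missing-data rule points towards removing it. Such an event is a failure to record, which is half of what section 3 sets out to establish. If these events leave the calculation, the reported sensitivity is unaffected by how many overdoses the system failed to record. A reader could take a high figure as evidence that the system works in this setting when it speaks only to the algorithm applied to the traces that exist.

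**Working it through.** **Inputs.** The protocol states no event rate, capture rate, expected sensitivity or power, and section 10.1 says that the target of around 50 participants is not based on a calculation. There is no planned figure to reproduce. The first step is therefore a reading of the text. The numbers after it are illustrations on assumed counts.

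**Step 1: follow one event through the plan.** Staff record a potential overdose in the case report form, and there is no usable trace.
- Section 10.3.2, index result: undefined, because it is derived from sensor data only.
- Section 10.3.2, reference result: cause for concern.
- Section 10.3.2, cells: no category exists for an absent recording. The false negative, the one cell in which the event could count as missed, is not named; true positive is listed twice. That is probably a slip, since sensitivity cannot be calculated without false negatives, and the point does not rest on it.
- Section 10.4: the staff record has no sensor data to reconcile with. If the exclusion covers all records, the event is excluded. If it covers sensor data only, the event still has no cell.

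**Step 2: which routes lead to no recording.** Non-wear and a stopped app or tablet are foreseen by the staff checks in section 4. An empty battery is possible between scheduled changes. Two other routes are weak. Section 7.4 expects the sensor to stay on during an intervention if it can, and the trace before the intervention would exist in any case. Loss of range is remote for events on site: the tablet is kept within range, the sensor is meant to be left behind when the participant goes out, and "The biosensor can continue to collect chest movement data while out of range of the tablet for 10-12 hours".

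**Step 3: the two measures.** Let N be all staff-recorded events in intended wear time, R those with a usable recording, and TP those recorded and flagged.
- Algorithm sensitivity = TP / R
- Capture = R / N
- System sensitivity = TP / N = (TP / R) × (R / N)

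The first does not involve N, so it does not respond to events that were never recorded.

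**Step 4: illustration, with Clopper-Pearson 95% intervals.**

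| Assumed N | Recorded R | Flagged TP | TP / R | TP / N |
|---|---|---|---|---|
| 10 | 7 | 7 | 100% (59% to 100%) | 70% (35% to 93%) |
| 20 | 12 | 11 | 92% (62% to 100%) | 55% (32% to 77%) |

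Check of one limit: for 7/7 the lower bound is 0.025^(1/7) = 0.59.

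**Step 5: range of the gap.** System sensitivity for assumed algorithm sensitivity and capture:

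| Algorithm sensitivity | Capture 100% | 90% | 80% | 70% | 60% | 50% |
|---|---|---|---|---|---|---|
| 80% | 80% | 72% | 64% | 56% | 48% | 40% |
| 90% | 90% | 81% | 72% | 63% | 54% | 45% |
| 100% | 100% | 90% | 80% | 70% | 60% | 50% |

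Over this assumed range of capture, an algorithm sensitivity of 90% is compatible with a system sensitivity anywhere from 45% to 90%.

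**The case against.** **The handling of non-evaluable results belongs in the SAP, which section 10.3 promises before data lock.** This would be decisive if the protocol were silent. It is not: section 10.3.2 fixes the comparison and section 10.4 fixes an exclusion rule. A SAP that follows both carries the gap forward.

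**The text never says that these events are dropped.** This stands in part. Someone might infer that they can never reach the denominator, but the protocol does not go that far. Scoring an absent recording as no alarm is not forbidden, and sensitivity is said to be calculated on the complete data set. Exclusion is the natural reading of the two sections together, not an express statement.

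**Capture is covered elsewhere.** Capturing chest motion is the primary objective, and compliance is assessed under section 8.4. However, compliance is taken from returned devices and is not linked to overdose events, so neither shows what share of the events was recorded.

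**Algorithm sensitivity is the right quantity for refining an algorithm.** This stands. Section 2 gives that purpose, and section 8.1 places the Alert algorithms outside the DC Mobile system. The measure should be kept. It does not by itself answer the recording part of section 3.

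**Stronger readings that the documents do not support.** A reader might infer that devices are more often off or not working when participants are heavily intoxicated, so that the lost events are selective. Nothing in the protocol documents this. A reader might also infer that one or two lost events would overturn the trial's conclusion. The protocol sets no sensitivity threshold, and the paired intervals above overlap widely. Finally, counting every event while a device is on issue would go too far, because section 4 tells participants to leave the sensor behind when they go out.

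**Conclusion.** The concern holds as a reading of sections 10.3.2 and 10.4 together. A staff-recorded potential overdose without a usable trace has no alarm status and no cell, and the missing-data rule points to exclusion. The planned sensitivity is then conditional on a recording. It remains a valid measure of the algorithm, but it cannot show whether the system records overdoses in this setting, and no other stated analysis links capture to those events.

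The size cannot be derived from the documents. The figures above rest on assumed event counts, assumed capture of 50% to 100% and assumed algorithm sensitivity of 80% to 100%. If every event is recorded, the two measures are equal and the gap has no numerical effect. The conclusion does not depend on any link between intoxication and missing data. The plan should be changed, because the gap concerns the stated aim and the remedy is cheap.

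**What to change.** Amend sections 10.3.2 and 10.4, and carry the rule into the SAP:

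1. Start from every potential overdose that staff record on site during a period when the participant holds an issued device and was meant to be wearing it. Do not exclude an event because sensor data are absent.
2. Report three proportions with exact 95% intervals: (a) capture, the share of these events with a usable recording before or at the event; (b) algorithm sensitivity among the recorded events; (c) system sensitivity among all of them, with no recording counted as not detected.
3. Give the reason for each uncaptured event, such as not worn, battery, or app or tablet not running.
4. List separately, outside all three proportions, events when no device was issued and events when the participant was off site with the device left behind as instructed.
5. Name the false negative cell in the list of categories.

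The cost is a few lines of text and two further proportions. The inputs are already planned: staff event records, the issue and return entries in the case report form (section 11.1), and the stored recordings. The downside is that system sensitivity can only be equal to or lower than algorithm sensitivity, so the report will carry a second figure that may be less favourable.
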